9.5 Surgical Procedure

9.5.1 Materials and Equipment

A listing of general equipment and materials needed for the preoperative, operative, and postoperative steps of the investigational study is provided below.

Goldmann Applanation Tonometer, Handheld direct ophthalmoscope, Viscoelastic Solution, Balanced Salt Solution, toothed forceps, tying forceps, non-toothed forceps, scissors, cautery, speculum, blades, punch, 25G or 23G needle and Ex-PRESS mini glaucoma shunt.

9.5.2 Surgical procedure

Ex-PRESS implantation procedure

Local or topical anesthesia is administered and the eye is prepared and covered using conventional sterile procedures. Implantation is performed using a special introducer, conventional microsurgical instruments and a surgical microscope.

The Ex-PRESS, mounted on its introducer is inserted into the anterior chamber at the limbus through the sclera under the scleral flap.

The implantation procedure may be performed as follows:

1. Creation of a fornix or limbal based conjunctival flap in the upper quadrants
2. Creation of a limbal-based scleral flap extending into clear cornea
3. Delicate application of MMC solution onto the sclerectomy bed. (MMC concentration 0.4mg/ml for 1-3 minutes)
4. Penetration into the anterior chamber using a 23-25G needle, halfway between the white sclera and the clear cornea (in the center of the grey zone), and creation of a track incision at the limbus
5. Prior to implantation, a thorough mobility check should be performed
6. Implantation of the Ex-PRESS implant loaded on its introducer, through that pre-incision
7. Withdrawal of the introducer
8. Tucking the plate under the scleral flap, and verification of its position
9. Suturing the scleral flap with sutures

After the implantation procedure, antibiotics and steroids are administered topically, the eye is covered with a pad and the patient is discharged.

Standard trabeculectomy procedure

1. Creation of a fornix or limbal based conjunctival flap in the upper quadrants
2. Creation of a limbal-based scleral flap extending into clear cornea
3. Delicate application of MMC solution onto the sclerectomy bed. (MMC concentration 0.4mg/ml for 1-3 minutes)
4. Creation of fistula 1mm x 2mm in size
5. Iridectomy
6. Suturing the scleral flap
7. Repositioning of the conjunctiva with sutures

After the procedure, antibiotics and steroids are administered topically, the eye is covered with a pad and the patient is discharged.

9.6 Follow up

All subjects will participate in defined follow-up visits for two years. Follow up visits include day of surgery, day 1, 1-2 Weeks, Months 1, 3, 6, 12, 18 and 24 post surgery. Additional visits will be performed and recorded as required for the optimal treatment and follow up of the patient. Additional visits are defined as visits that were not preplanned and considered emergent. Table 1 presents the activities to be performed at each follow up visit.

Table 1: Follow-up Activities

Activity	Screening	Surgery	1 Day	1-2 Wk	1 Mo	3 Mo	6 Mo	12 Mo	18 Mo	24 Mo
Ophthalmology Exam	X									
Medical History	X									
Medication Assessment	X		X	X	X	X	X	X	X	X
Visual Field	X							X		X
CD ratio	X							X		X
Slit-lamp Exam	X		X	X	X	X	X	X	X	X
Visual Acuity	X		X	X	X	X	X	X	X	X
Fundus Exam	X							X		X
IOP	X		X	X	X	X	X	X	X	X
Procedure		X								
Adverse Event Assessment		X	X	X	X	X	X	X	X	X
Protocol Deviation Assessment		X	X	X	X	X	X	X	X	X

- Intraocular pressure measurements during follow-up visits

Each time IOP is measured, the surgeon or technician is to utilize a Goldmann tonometer, however, an independent observer should read the measurement and then record the measurement to minimize observer bias.

Two measurements should be taken and the mean recorded on the case report form UNLESS they differ by more than 2 mmHg in which case a third measurement is taken and the median value is recorded.

All attempts should be made to conduct each follow-up evaluation within the specified time intervals (Table 2).

Table 2: Follow up examination schedule

Follow up visit	Acceptable Time Interval (Days from Procedure)
Day 1 pos-op	Day 1 post op
7-14 days post-op	7-14 days post-op
1 month post-op	30 days \pm 7 days
3 months post-op	90 days \pm 14 days
6 months post-op	180 days \pm 21 days
12 months post-op	360 days \pm 30 days
18 months post-op	540 days \pm 30 days
24 months post-op	720 days \pm 30 days

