3.0 Rationale for the Study

Trabeculectomy has been the surgical treatment of choice for primary open angle glaucoma since 1970s (1), its success rates and complications however are less than ideal. Early hypotony and bleb infections are still of concern.

The Ex-PRESS, a miniature stainless steel glaucoma device approved by FDA since March 2002, is widely used worldwide for open angle glaucoma patients. This procedure is theoretically more reproducible and simple to perform as well as less traumatic to the ocular tissue than traditional filtering surgery.

With regard to the inclusion of subjects diagnosed and being treated for ocular hypertension, several recently published studies demonstrate that in patients with elevated IOP, with or without the visual field loss or optic nerve damage of glaucoma, lowering IOP provides benefit in long-term outcome of subsequent visual field loss (2-5). In any case, all subjects enrolled in the study have the opportunity to be treated with ocular hypotensive medications during the follow-up period as judged appropriate by the investigator.

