7.3 Primary Safety End Points

Post operative safety profile defined as vitreous loss and hypotony ($IOP \leq 5 \text{ mmHg}$) and related complications (choroidal effusion, hyphema, shallow/flat AC, leaking bleb).

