8.0 Study Claim

The safety of the Ex-PRESS™ is superior and efficacy as good as trabeculectomy in open angle glaucoma patients.

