9.0 Study Protocol

9.1 Study Synopsis

Title:	A prospective randomized multi-center study to compare the Ex-PRESS™ to trabeculectomy in patients with open angle glaucoma who failed medical treatment and for which filtering surgery is indicated
Protocol Number:	XVT-01
Number of Sites:	7 sites were approved.
Study Period:	2 year, 10 visits: Pre-operation, day of surgery, day 1, 1-2 Weeks, Months 1, 3, 6, 12, 18 and 24 post operation. Additional visits will be performed and recorded as required for the optimal treatment and follow up of the patient. Additional visits are defined as visits that were not preplanned and considered emergent.
Study design:	A prospective, two arm, active control, unmasked, randomized study
Objectives:	A prospective randomized trial to compare the safety and efficacy of the Ex-PRESS to trabeculectomy in patients with open angle glaucoma who failed medical or are allergic to medical treatment and for which filtering surgery is indicated
Control Arm	Subjects undergoing trabeculectomy with the use of Mitomycin C
Treatment Arm	Subjects undergoing Ex-PRESS Under Scleral Flap implantation procedure with the use of Mitomycin C
Subject Population:	Open angle glaucoma patient's candidates for filtering surgery. The patients may have a history of cataract phacoemulsification surgery.
Sample Size:	Total of 120 subjects with 60 subjects in each arm. Each site can enroll a maximum of 30 subjects and a minimum of 5 subjects for each study arm.
Follow-up duration:	2 years
Target enrollment period:	Up to 1 year

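### Detection of early hypotony depends on how often an eye is examined, and the plan neither records all unscheduled visits clearly nor allows for unequal examination between unmasked arms

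*Combined protocol and SAP*

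**What the plan says.** - Section 3.0 gives part of the motivation: "Early hypotony and bleb infections are still of concern".
- Section 7.3 defines the primary safety end point: "Post operative safety profile defined as vitreous loss and hypotony" (IOP of 5 mmHg or less) "and related complications (choroidal effusion, hyphema, shallow/flat AC, leaking bleb". It gives no time window, set of visits or counting rule.
- Section 8.0 claims that the safety of the device "is superior and efficacy as good as trabeculectomy in open angle glaucoma patients".
- The synopsis (9.1) describes the design as "A prospective, two arm, active control, unmasked, randomized study".
- Section 9.6, Tables 1 and 2, places post-operative IOP at day 1, at one visit labelled "7-14 days post-op", at 30 ± 7 days, and later. Table 1 has no IOP mark on the day of surgery.
- On visits outside that schedule, 9.6 says "Additional visits will be performed and recorded as required for the optimal treatment and follow up of the patient", and then "Additional visits are defined as visits that were not preplanned and considered emergent". The synopsis repeats both sentences.
- Section 12.0 names Fisher's exact test but does not say which visits supply the hypotony count.

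**The concern.** Whether an eye is ever recorded at 5 mmHg or less depends on its true pressure course and on how often it is measured. The schedule fixes two early measurements per eye. The rest depend on decisions to bring a patient back and on whether that visit is treated as an additional visit under 9.6. Those decisions can be made with knowledge of the arm. If one arm is seen more often, it can show more hypotony at equal true risk.

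The definition in 9.6 adds a recording question. A recheck booked in advance and not regarded as emergent fits the first sentence of the rule but not the second. Sites could differ on whether its IOP belongs in the study data.

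At stake is the interpretability of one component of the primary safety comparison, on which the superiority claim partly rests. The independent-observer rule for tonometry limits bias in a reading that is taken. It does nothing about how many are taken.

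**Working it through.** **Scheduled readings.** The month 1 window opens on day 30 − 7 = 23 and closes on day 30 + 7 = 37. The only earlier scheduled post-operative IOP visits are day 1 and one in days 7–14. So two recorded values per eye fall before day 23, and still only two before day 37 if the month 1 visit is late. The gap can be 14 − 1 = 13 days between the first two visits and 37 − 7 = 30 days between the second and third.

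**What the documents do not supply.** They give no hypotony rate, visit frequency by arm, alpha or power. Only the 60 eyes per arm and the Fisher test come from the plan. Every other input below is an assumption.

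**Simplest illustration.** Let 30% of eyes in both arms have hypotony only between scheduled visits, found only if an extra visit is recorded. Detected rate = 0.30 × probability of an extra visit:
- 0.30 × 0.20 = 6%
- 0.30 × 0.40 = 12%
- 0.30 × 0.60 = 18%

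Exact enumeration of the two-sided Fisher test (60 per arm, alpha 0.05) gives a significant result in 12% of trials for 6% v 12%, 42% for 6% v 18%, and 1.4% for 6% v 6%. This overstates the contrast, because it leaves out hypotony found at scheduled visits in both arms.

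**With scheduled detection included.** Let *s* be the share of eyes found hypotonous at scheduled visits, *h* the share of the remaining eyes with a between-visit episode, and *v* the probability of an extra visit that catches it. Detected rate = *s* + (1 − *s*) × *h* × *v*, with *s* and *h* equal in both arms. For *s* = 10%, *h* = 40%, *v* = 20%: 0.10 + 0.90 × 0.40 × 0.20 = 17.2%.

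| *s* | *h* | Detected at *v* = 20% / 40% / 60% | False positive, 20% v 40% | False positive, 20% v 60% | Scheduled readings only |
|---|---|---|---|---|---|
| 10% | 20% | 13.6 / 17.2 / 20.8% | 5.0% | 12.2% | 2.2% |
| 10% | 40% | 17.2 / 24.4 / 31.6% | 11.1% | 36.9% | 2.2% |
| 20% | 20% | 23.2 / 26.4 / 29.6% | 4.3% | 8.6% | 2.8% |
| 20% | 40% | 26.4 / 32.8 / 39.2% | 8.3% | 25.2% | 2.8% |

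The ranges are therefore about 4–11% and 9–37%, against 2–3% when detection is equal.

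**A second model.** Suppose 20–50% of eyes have one episode of 3 or 7 days starting in days 0–21. Two extra early visits in one arm only then give 7–33%, against 0.6–2.8% with no extra visits in either arm. That imbalance is severe, so these figures are a stress case.

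**The case against.** **Recording is largely covered elsewhere.** A reader might infer that leaks or shallow chambers seen at a booked recheck would be lost. The documents do not support that. Section 11.1 requires any ocular adverse event to go on CRF 4 whatever the visit, 11.2 repeats this for all adverse events, 10.3 makes CRF 3 the form for all follow-up visits, and 11.0 has abnormalities noted at each visit. This objection stands. What remains exposed on recording is mainly an isolated low IOP that nobody calls an adverse event. Section 7.4 does promise that all measurements will be collected and analysed, but it does so under IOP spikes.

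**The two sentences in 9.6 need not conflict.** The second may simply define the first as unscheduled visits arising from clinical need. That reading is possible, but the text allows the narrower one as well.

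**Several details are inferred.** Section 9.6 does not say who judges a visit emergent, and no section says that scheduled and extra readings are pooled. It is tempting to state both as fact, but the plan is silent, and that silence is what needs repair.

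**Direction is unknown.** A reader might infer a push towards the device. Nothing in the documents shows which arm would be seen more often. The two mechanisms also oppose each other: unrecorded rechecks remove events from the arm watched more closely, while recorded extra visits add them.

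**The size is assumed and can be small.** In the simplest illustration, 6% v 12% is about 4 v 7 of 60 (Fisher p = 0.53), and 6% v 18% is about 4 v 11 (p = 0.095). With six scheduled-visit cases added per arm, p is 0.64 and 0.19. So a typical result under these inputs would not be significant. The false-positive rate is still raised.

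**A scheduled-only primary count has its own cost.** It would drop real hypotony found between visits and could dilute a true difference. This stands, and it argues for showing both analyses.

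**Conclusion.** The plan leaves open an ascertainment bias in one component of its primary safety comparison. Complete recording alone would not close it, because detection still rises with the number of examinations. The documents establish the two scheduled early readings, the unmasked design, the superior-safety claim and the absence of any rule for unequal examination. They do not establish that visits will differ by arm, which arm would gain, or by how much. The false-positive rates of about 4–11% and 9–37% rest on assumed detection rates, assumed visit imbalances and an assumed two-sided 0.05 level. Moderate imbalance does modest harm, and large imbalance does serious harm.

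Hypotony is not the only thing the trial measures. Section 7.3 also lists vitreous loss and related complications, 3.0 also names bleb infections, and the primary effectiveness end point is IOP of 18 mmHg or less at 12 months. The point is a cheap improvement worth making and does not invalidate the design.

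**What to change.** 1. In 9.6, and where the synopsis repeats it, delete the condition that an additional visit be considered emergent. Require CRF 3, including IOP, for every visit concerning the study eye outside Table 2, planned or not.
2. In 7.3 and 12.0, report the hypotony comparison twice: on all recorded readings, and on Table 2 scheduled readings only. State that any superiority conclusion on hypotony will be interpreted against both.
3. Tabulate by arm the number of unscheduled visits per eye and the 7.3 events found only at such visits.

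The cost is a few more CRF 3 pages, one extra table and one extra analysis. The scheduled-only count will be lower than the all-readings count, which is why neither should stand alone. No change to the visits or care that patients receive is proposed.

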7.1 Primary Effectiveness End Points

The primary effectiveness measure will be qualified and complete success rate defined as $IOP \leq 18 \text{ mmHg}$ with or without medications in the test group as compared to complete and qualified success rate in the concurrent control group at 12 months.

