11.0 Safety

At each visit, the ocular health of each subject will be assessed. The cornea, anterior chamber, trabecular meshwork, and implant location (if applicable) will be examined. If any abnormalities are observed, they are to be noted (type and location) within the case report forms.

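### Sections 9.4.2 and 9.6 give IOP a second, independent reader but do not mask that reader to arm or keep the operator from the dial, so threshold endpoints stay open to expectation bias that could be reduced.

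*Combined protocol and SAP*

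**What the plan says.** The synopsis (section 9.1) describes "A prospective, two arm, active control, unmasked, randomized study". The IOP procedure is given in the same words at baseline (9.4.2) and at follow-up (9.6). It involves two people:

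- **Operator.** "Each time IOP is measured, the surgeon or technician is to utilize a Goldmann tonometer".
- **Reader and recorder.** "an independent observer should read the measurement and then record the measurement to minimize observer bias".

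Replicates are specified: "Two measurements should be taken and the mean recorded on the case report form UNLESS they differ by more than 2 mmHg". A wider gap calls for another reading, and the median is then used.

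The primary effectiveness endpoint (7.1) counts a reading of 18 mmHg or below as success: "with or without medications in the test group as compared to complete and qualified success rate in the concurrent control group at 12 months". Section 7.2 applies the same cut at 24 months. Section 7.3 includes hypotony, at or below 5 mmHg, in primary safety. Section 7.4 counts IOP spikes, a rise of at least 10 mmHg from baseline.

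**The concern.** The sponsor has named observer bias as a risk and assigned a second person to control it. Separating the two roles does only part of that job. With a Goldmann instrument the operator turns a dial to an end point judged by eye. An operator who knows the arm and can see the scale can stop near an expected value, and the independent reader then records that value faithfully. A reader who knows the arm can also round towards expectation. The text as written prevents neither.

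At stake are the two effectiveness endpoints and primary hypotony, all of which are cuts on this one reading. The study claim (8.0) has a direction: superior safety and "efficacy as good as trabeculectomy in open angle glaucoma patients". A shift favouring one arm would feed straight into the comparison behind that claim.

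**Working it through.** **1. The text, side by side.**

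| Question | What the plan says |
|---|---|
| Is any role masked? | None is described as masked; 9.1 says unmasked |
| Does the operator know the arm? | The operator may be the surgeon. At each visit "implant location (if applicable) will be examined" (11.0), and only the trabeculectomy steps in 9.5.2 list an iridectomy |
| Is the operator kept from the dial? | Not stated |
| Is the dial reset between readings? | Not stated |
| Is the reader unaware of the arm? | Not stated; *independent* is not defined |
| Does replication help? | It limits random error and isolated outliers, not a consistent shift |

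**2. No plan figure to reproduce.** The only design number is 120 subjects, 60 per arm. Section 12.0 names Fisher's exact test but gives no alpha, power, expected rates or margin. The plan gives no IOP mean or SD. All inputs below except the 18 mmHg cut and 60 per arm are therefore assumptions.

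**3. Effect of a reading shift on the success rate.** Assume 12-month IOP is normal with mean m (13-15) and SD s (3-5 mmHg). The success rate is S = Φ((18 − m)/s). A shift of b mmHg in one arm changes it by:

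- readings too low: Φ((18 − m + b)/s) − Φ((18 − m)/s)
- readings too high: Φ((18 − m)/s) − Φ((18 − m − b)/s)

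Mid-range example, m = 14, s = 4: S = Φ(1.00) = 84.1%. Reading 1 mmHg low gives Φ(1.25) = 89.4%, a gain of 5.3 points. Reading 1 mmHg high gives Φ(0.75) = 77.3%, a loss of 6.8 points. With 60 per arm, 5.3 points is 0.053 × 60 ≈ 3 patients.

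Range for means 13, 14, 15 and SDs 3, 4, 5:

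| Shift | Readings too low | Readings too high | Either direction |
|---|---|---|---|
| 0.5 mmHg | 1.4-3.7 points | 1.9-4.4 points | 1.4-4.4 points |
| 1 mmHg | 2.5-6.8 points | 4.3-9.4 points | 2.5-9.4 points |

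The smallest changes come from m = 13, s = 3, reading low: 96.66 − 95.22 = 1.44 and 97.72 − 95.22 = 2.50. The largest come from m = 15, s = 3, reading high: 84.13 − 79.77 ≈ 4.4 and 84.13 − 74.75 = 9.38.

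**4. Effect on Fisher's test.** Exact enumeration with 60 per arm, an assumed two-sided 5% level, no true difference, m = 14, s = 4: rejection is 2.7% with no shift. It is 8.4% if one arm reads 1 mmHg low (84.1% against 89.4%) and 10.5% if one arm reads 1 mmHg high (84.1% against 77.3%).

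**5. Effect on an *as good as* claim.** The plan states no margin. Assume margins of 10-20 points, m = 14-15 in the control arm, s = 4, and a true deficit equal to the margin. Non-inferiority is concluded when the lower 95% Wald limit clears the margin. That wrong conclusion occurs in 2.5-2.9% of trials with no shift, 8.5-9.3% if the device arm reads 0.5 mmHg low, and 20-24% if it reads 1 mmHg low.

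No calculation was made for the 5 mmHg hypotony cut. The mechanism is the same, but its size is not estimated here.

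**The case against.** The strongest reply is that the main safeguard is already there. The plan separates operator from reader expressly to limit observer bias, replicates the readings, and says openly that it is unmasked. What is left is a refinement of an existing control. That stands, and it sets the weight of the point.

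Several stronger readings are tempting, and the documents do not support them:

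- **That the reader knows the arm.** The plan is silent on what the reader knows.
- **That the bias could be removed.** The operator still aligns the tonometer on an eye whose arm may be visible. The endpoint also counts success on medication, and subjects may be "treated with ocular hypotensive medications during the follow-up period as judged appropriate by the investigator" (3.0), in a trial where the investigator is not masked. The fix does not touch that route.
- **That no extra staff would be needed anywhere.** A second person is already specified, so existing staff will probably suffice. But staffing is not described, and nothing shows that each of the 7 sites has a reader unaware of the arm at months 12 and 24.
- **That *should* makes the second reader optional.** Section 9.6 uses the same verb for taking two measurements and keeping visit windows. It looks like house style and is weak evidence of an optional step.
- **That the results will be shifted by the amounts shown.** Nothing in the documents indicates that a systematic difference of 0.5 or 1 mmHg would survive the two-person procedure.

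**Conclusion.** The point holds as a low-cost improvement. The plan specifies a second reader, but it neither masks that reader nor keeps an operator who may know the arm from seeing the scale. The 18 mmHg endpoints and the 5 mmHg hypotony endpoint therefore stay open to expectation bias that could be reduced.

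The 1.4-4.4 and 2.5-9.4 point ranges rest on assumed normal IOP distributions and a constant shift confined to one arm. They show how sensitive a cut at 18 mmHg is to small reading errors. They do not estimate the bias in this trial.

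**What to change.** In both 9.4.2 and 9.6, state that:

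- the operator must not see the dial, and the dial is reset before each reading;
- the reader sees only the dial, and is not told the arm or shown the eye or chart;
- the reader writes each value on a separate slip or IOP page, for later transfer to the case report form, and calls for a third reading when the first two differ by more than 2 mmHg;
- where a site has no reader unaware of the arm, the hidden dial and the reset still apply;
- at months 12 and 24, where a technician is already available, the technician and not the treating surgeon operates the tonometer.

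Phrase these as requirements, using the two people already specified. The cost is protocol wording, brief site training and some scheduling to find a reader who does not know the arm. Visits, sample size, treatment and analysis are unchanged.
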